2.5 Rationale

We hypothesize that co-administration of the MET inhibitor ARQ 197 will prevent the adaptive response to hypoxia resulting from treatment with the VEGFR inhibitor pazopanib, and conversely, that co-administration of pazopanib will prevent the effect of increased VEGF and reduced TSP-1 in tumors after treatment with ARQ 197. Therefore, the combination of these agents may result in improved antitumor effects.

3 PATIENT SELECTION

3.1 Eligibility Criteria

- 3.1.1** Patients with histologically confirmed (by the Laboratory of Pathology, NIH) solid tumors that have progressed following at least one line of standard therapy or for whom no standard treatment options exist.
- 3.1.2** Patients must have measurable or evaluable disease.
- 3.1.3** Patients enrolling in the expansion cohorts must have disease amenable to biopsy, and be willing to undergo pre-and post-treatment biopsies.
- 3.1.4** Patients must have completed any chemotherapy, radiation therapy, or biologic therapy \geq 4 weeks prior to entering the study (6 weeks for nitrosoureas or mitomycin C). Patients must be \geq 2 weeks since any prior administration of a study drug in a phase 0 or equivalent study. Patients must have recovered to

eligibility levels from prior toxicity or adverse events. Treatment with bisphosphonates is permitted.

- 3.1.5** Patients who have had prior treatment with any anti-angiogenic therapy and/or c-MET inhibitor are eligible in the dose escalation phase unless the anti-angiogenic therapy and/or c-MET inhibitor were administered within the 4 weeks prior to entering the study. In the expansion phase, prior c-MET inhibitor is not allowed, and anti-angiogenic therapy is not allowed within the 3 months prior to entering the study.
- 3.1.6** Age \geq 18 years. Because no dosing or adverse event data are currently available on the use of pazopanib in combination with ARQ 197 in patients $<$ 18 years of age, children are excluded from this study.
- 3.1.7** Life expectancy $>$ 3 months.
- 3.1.8** ECOG performance status 0 or 1 (see [Appendix A](#)).
- 3.1.9** Patients must have normal organ and marrow function as defined below:
- Absolute neutrophil count \geq 1,500/ μ L
 - Platelets \geq 100,000/ μ L
 - Total bilirubin \leq 1.5 X institutional ULN
 - AST (SGOT)/ALT (SGPT) \leq 2.5 X institutional ULN
 - Creatinine \leq 1.5 mg/dL (133 μ mol/L); OR
 - Measured creatinine clearance \geq 60 mL/minute for patients with creatinine levels $>$ 1.5 mg/dL
 - Urine protein/creatinine ratio $<$ 1 OR
24-hour urine protein $<$ 1 gram

Subjects who have both bilirubin $>$ ULN and AST/ALT $>$ ULN are not eligible.

- 3.1.10** Subjects in the expansion cohort must have PT/INR/PTT \leq 1.2 X institutional ULN, except patients with confirmed positive lupus anticoagulant test.
- 3.1.11** Subjects must have blood pressure (BP) no greater than 140 mmHg (systolic) and 90 mmHg (diastolic) for eligibility. Initiation or adjustment of BP medication is permitted prior to study entry provided that the average of three BP readings at a visit prior to enrollment is less than 140/90 mmHg.
- 3.1.12** The effects of study drugs on the developing human fetus are unknown. For this reason, women of child-bearing potential and men must agree to use adequate contraception (hormonal or barrier method of birth control; abstinence) prior to study entry, for the duration of study participation, and for at least 2 months after dosing with study drugs ceases. Should a woman become pregnant or suspect she

is pregnant while she or her partner is participating in this study, she should inform her treating physician immediately. Women of child-bearing potential must have a negative pregnancy test prior to entry.

3.1.13 Patients must be able to swallow whole tablets or capsules. Nasogastric or G-tube administration is not allowed.

3.1.14 Ability to understand and the willingness to sign a written informed consent document.

3.2 Exclusion Criteria

3.2.1 Patients who are receiving any other investigational agents.

3.2.2 Patients with active brain metastases or carcinomatous meningitis are excluded from this clinical trial. Patients whose brain metastatic disease status has remained stable for ≥ 4 weeks following treatment of the brain metastases are eligible to participate.

3.2.3 History of allergic reactions attributed to compounds of similar chemical or biologic composition to pazopanib or ARQ 197.

3.2.4 Eligibility of subjects receiving any medications or substances known to affect or with the potential to affect the activity or pharmacokinetics of pazopanib or ARQ 197 will be determined following review of their cases by the Principal Investigator (see Sections 3.2.5-3.2.6 for further information). Efforts should be made to switch subjects with gliomas or brain metastases who are taking enzyme-inducing anticonvulsant agents to other medications.

3.2.5 Certain medications that act through the CYP450 system are specifically prohibited in subjects receiving pazopanib and ARQ 197 and others should be avoided or administered with extreme caution.

- **Strong inhibitors of CYP3A4** such as ketoconazole, itraconazole, clarithromycin, atazanavir, indinavir, nefazodone, nelfinavir, retonavir, saquinavir, telithromycin, voriconazole may increase pazopanib concentrations and **are prohibited; although, in exceptional circumstances they may be administered in conjunction with lowering the dose of pazopanib by 50%** of what would otherwise be administered. Grapefruit juice is also an inhibitor of CYP450 and should not be taken with pazopanib.
- **Strong inducers of CYP3A4**, such as rifampin, may decrease pazopanib concentrations, **are strictly prohibited**. (See [Appendix B](#))
- **Medications which have narrow therapeutic windows and are substrates of CYP3A4, CYP2D6, or CYP2C8** should be avoided and, if necessary, administered **with caution**. (See [Appendix B](#))

- **Inhibitors or inducers of CYP2C19** should be avoided and, if necessary, administered **with caution**. (See [Appendix B](#))

3.2.6 Cardiovascular baseline QTc \geq 480 msec will exclude patients from entry on study. Medications that may cause QTc interval prolongation are listed in [Appendix C](#), and should be avoided by patients entering on trial. Patients for whom a given medication that may cause QTc interval prolongation cannot be discontinued may be eligible at the discretion of the study PI. A comprehensive list of agents with the potential to cause QTc prolongation can be found at <http://www.azcert.org/medical-pros/drug-lists/bycategory.cfm>. (Note: If subjects must take medications with a risk or possible risk of Torsades de Pointes, they should be watched carefully for symptoms of Torsades de Pointes, such as syncope. Performing additional EKGs on subjects who must take one or more of these medications is not required; however, additional investigations, including EKGs, may be performed as per the treating physician's judgment.)

3.2.7 Subjects with any of the following cardiovascular conditions within the past 6 months:

- cerebrovascular accident (CVA) or transient ischemic attack (TIA)
- clinically significant bradycardia or other uncontrolled cardiac arrhythmia
- admission for unstable angina or myocardial infarction
- cardiac angioplasty or stenting
- coronary artery bypass graft surgery
- pulmonary embolism, untreated deep venous thrombosis (DVT) or DVT which has been treated with therapeutic anticoagulation for less than 6 weeks
- arterial thrombosis
- symptomatic peripheral vascular disease
- Class III or IV heart failure as defined by the NYHA functional classification system (see [Appendix D](#)). A subject who has a history of Class II heart failure and is asymptomatic on treatment may be considered eligible

3.2.8 History of serious or non-healing wound, ulcer, or bone fracture.

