5.3 General Concomitant Medication and Supportive Care Guidelines

All patients will be provided with the best available supportive care. All concurrent medications should be documented prior to initiation of treatment, and be periodically reviewed with the patient. Particular attention must be paid to medications which may prolong the QTc interval ([Appendix C](#)) and agents that interact with CYP450 isoenzymes ([Appendix B](#)).

QTc Prolongation:

Caution should be exercised when administering pazopanib to patients with a history of QTc interval prolongation, in patients taking anti-arrhythmics or other medications that may prolong the QTc interval, and those with relevant pre-existing cardiac disease. A list of medications that may cause QTc interval prolongation are listed in [Appendix C](#), and should be avoided by patients on this study. EKG will be performed as described in [Section 5](#). If the QTc interval on follow-up EKG is ≥ 500 msec, the EKG should be repeated within 7 days and, if the QTc interval remains ≥ 500 msec, the subject should be removed from the study. Additionally, if the QTc interval is increased by 60 msec or more from baseline but the QTc interval remains at <500 msec, the EKG should be repeated within 7 days. If the repeat EKG again shows a ≥ 60 msec increase in the QTc interval from baseline, consideration should be given to removing

the subject from the study or increasing monitoring, after discussion with the principal investigator.

CYP450 Interactions:

In vitro and in vivo animal data indicate that the metabolism of pazopanib is primarily mediated by CYP3A4. In vitro data indicate that pazopanib is a potential inhibitor for CYP2C9, CYP1A2, CYP2A6, CYP2B6, CYP2C8, CYP2C19, CYP2D6, CYP2E1, and CYP3A4. In addition, one in vitro study suggested that pazopanib may induce CYP3A4 at high concentrations. Potent CYP3A4 inhibitors and inducers are prohibited on pazopanib trials. In exceptional circumstances, medications which strongly inhibit CYP3A4 may be administered, with caution, if the dose of pazopanib is decreased to 50% of the dose which would otherwise be administered.

Medications that strongly inhibit CYP3A4 include (but are not limited to):

- Antibiotics: clarithromycin, telithromycin, troleandomycin
- HIV: protease inhibitors (ritonavir, indinavir, saquinavir, nelfinavir, amprenavir, lopinavir)
- Antifungals: itraconazole, ketoconazole, voriconazole
- Antidepressant: nefazodone

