Grapefruit juice is also an inhibitor of CYP450 and should not be taken with pazopanib.

Medications that strongly induce CYP3A4 include (but are not limited to):

- Glucocorticoids: cortisone (>50 mg), hydrocortisone (>40 mg), prednisone (>10 mg), methylprednisolone (>8 mg), dexamethasone (>1.5 mg)
- Anticonvulsants: phenytoin, carbamazepine, phenobarbital, oxcarbazepine
- HIV antivirals: efavirenz, nevirapine
- Antibiotics: rifampin (rifampicin), rifabutin, rifapentene
- Miscellaneous: St. John's Wort, modafinil, pioglitazone, troglitazone

Pazopanib is a weak inhibitor of CYP3A4, CYP2C8, and CYP2D6. Drugs that have narrow therapeutic windows and are substrates for these enzymes should be avoided and, if necessary, administered with caution (see [Appendix B](#)). Because of pazopanib's long half-life, caution should continue to be exercised for at least 7 days and up to 15 days after the last dose of pazopanib when administering these medications.

Medications that are substrates for these enzymes *and* have narrow therapeutic windows medications include (but are not limited to):

- Ergot derivatives: dihydroergotamine, ergonovine, ergotamine, methylergonovine (potential increased risk for developing ergot toxicity that includes severe vasospasm leading to peripheral as well as cerebral ischemia)
- Neuroleptics: pimozide (potential increased risk for QT interval prolongation, ventricular arrhythmia, and sudden death)
- Antiarrhythmics: bepridil, flecainide, lidocaine, mexiletine, amiodarone, quinidine, propafenone (potential increased risk for QT interval prolongation and Torsade de Pointes)
- Immune modulators: cyclosporine, tacrolimus, sirolimus (potential increased risk for nephrotoxicity and neurotoxicity)
- Miscellaneous: quetiapine, risperidone, clozapine, atomoxetine

In vitro studies indicate ARQ 197 is metabolized by CYP2C19, and to a lesser extent CYP3A4. The metabolism and consequently overall pharmacokinetics of ARQ 197 could be altered by inhibitors and/or inducers or other substrates of CYP2C19 and CYP3A4. In patients receiving any medications or substances that are inhibitors or inducers of CYP3A4 or CYP2C19, every attempt should be made to change the medications to another agent that does not affect the CYP pathway (see [Appendix B](#)).

Specific recommendations regarding other oral hypoglycemics:

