Amlodipine	Delavirdine	Hydralazine	Nevirapine	Saquinavir
Amprenavir	Desipramine	Ifosfamide	Nicardipine	Selegiline
Anastrozole	Dexmedetomidine	Imatinib	Nifedipine	Sertraline
Aprepitant	Diazepam	Indinavir	Nisoldipine	Sildenafil
Atazanavir	Diclofenac	Irbesartan	Nizatidine	Sirolimus
Atorvastatin	Dihydroergotamine	Isoniazid	Norfloxacin	Sulconazole
Azelastine	Diltiazem	Isradipine	Olanzapine	Tacrolimus
Azithromycin	Disulfiram	Itraconazole	Omeprazole	Tamoxifen
Betamethasone	Docetaxel	Ketoconazole	Orphenadrine	Telithromycin
Bortezomib	Doxorubicin	Lansoprazole	Oxybutynin	Teniposide
Bromocriptine	Doxycycline	Lidocaine	Paroxetine	Testosterone
Caffeine	Drospirenone	Lomustine	Pentamidine	Tetracycline
Cerivastatin	Efavirenz	Losartan	Pergolide	Ticlopidine
Chloramphenicol	Enoxacin	Lovastatin	Phencyclidine	Tranlycypromine
Chlorzoxazone	Entacapone	Mefloquine	Pilocarpine	Trazodone
Cimetidine	Ergotamine	Mestranol	Pimozide	Troleandomycin
Ciprofloxacin	Erythromycin	Methadone	Pravastatin	Valproic acid
Cisapride	Ethinyl estradiol	Methimazole	Prednisolone	Venlafaxine
Clarithromycin	Etoposide	Methoxsalen	Primaquine	Verapamil
Clemastine	Felodipine	Methylprednisolone	Progesterone	Vinblastine
Clofazimine	Fentanyl	Metronidazole	Propofol	Vincristine
Clotrimazole	Fluconazole	Miconazole	Propoxyphene	Vinorelbine
Clozapine	Fluoxetine	Midazolam	Quinidine	Voriconazole
Cocaine	Fluvastatin	Mifepristone	Quinine	Zafirlukast
Conivaptan	Fluvoxamine	Mirtazapine	Quinupristin	Ziprasidone
Cyclophosphamide	Fosamprenavir	Mitoxantrone	Rabeprazole	

CYP3A4 Inducers

Aminoglutethimide	Nafcillin	Pentobarbital	Primidone	Rifapentine
Carbamazepine	Nevirapine	Phenobarbital	Rifabutin	St. John's wort (3)
Fosphenytoin	Oxcarbazepine	Phenytoin	Rifampin	

CYP3A4 Substrates

Albuterol	Docetaxel	Ketoconazole	Quetiapine
Alfentanil	Doxepin	Lansoprazole	Quinidine
Alprazolam	Doxorubicin	Letrozole	Rabeprazole
Amlodipine	Doxycycline	Levomethadyl acetate hydrochloride	Repaglinide
Amprenavir	Efavirenz	Levonorgestrel	Rifabutin
Aprepitant	Eletriptan	Lidocaine	Rifampin
Aripiprazole	Enalapril	Losartan	Ritonavir
Atazanavir	Eplerenone	Lovastatin	Saquinavir
Atorvastatin	Ergoloid mesylates	Medroxyprogesterone	Sertraline
Benzphetamine	Ergonovine	Mefloquine	Sibutramine
Bisoprolol	Ergotamine	Mestranol	Sildenafil
Bortezomib	Erythromycin	Methadone	Simvastatin
Bosentan	Escitalopram	Methylergonovine	Sirolimus
Bromazepam	Estradiol	Methysergide	Sufentanil
Bromocriptine	Estrogens, conj., synthetic	Miconazole	Tacrolimus

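### The 3.2.5 ban on strong CYP3A4 inducers points to an Appendix B table that omits 9 of the 18 agents named in Section 5.3, which creates a screening-error risk

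*Combined protocol and SAP*

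**What the plan says.** Four places in the protocol bear on inducers.

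- **Section 3.2.5** (exclusion criteria) says that strong CYP3A4 inducers "may decrease pazopanib concentrations, are strictly prohibited". Rifampin is the only example, and the reader is referred to Appendix B.
- **Section 3.2.4** leaves eligibility of patients on drugs that may affect the activity or pharmacokinetics of either agent to case review by the Principal Investigator, with a pointer to 3.2.5 and 3.2.6. It adds: "Efforts should be made to switch subjects with gliomas or brain metastases who are taking enzyme-inducing anticonvulsant agents to other medications".
- **Section 5.3** states: "Potent CYP3A4 inhibitors and inducers are prohibited on pazopanib trials". It then gives an open list, introduced by "Medications that strongly induce CYP3A4 include (but are not limited to", whose groups include "Glucocorticoids: cortisone (>50 mg), hydrocortisone (>40 mg), prednisone (>10 mg), methylprednisolone (>8 mg), dexamethasone (>1.5 mg", "Anticonvulsants: phenytoin, carbamazepine, phenobarbital, oxcarbazepine" and "HIV antivirals: efavirenz, nevirapine", plus three antibiotics and four miscellaneous agents. Further down, for patients on CYP3A4 or CYP2C19 inhibitors or inducers, it asks that every attempt be made to change the drug. Section 5.3 also directs readers to Appendix B for drugs that interact with CYP450 enzymes.
- **Appendix B** has a table headed "CYP3A4 Inducers" with 14 entries, and a longer CYP3A4 inhibitor table. A note says that the inducers shown are the effective ones. The inducer table gives no strength grading and no glucocorticoid dose thresholds.

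**The concern.** The eligibility criterion sends the reader to a table that does not match the protocol's own list of strong inducers. A screener who checks a patient on dexamethasone above 1.5 mg against Appendix B finds nothing. The same check against 5.3 finds a prohibited drug. The note that only effective inducers are shown invites the reader to treat absence as clearance. For three agents Appendix B also implies the opposite direction of effect, because it says that inhibitors may raise and inducers may lower concentrations of the study drugs.

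A second ambiguity does not depend on the tables. The four anticonvulsants in 5.3 are strong inducers and so fall under the 3.2.5 ban, yet 3.2.4 asks only for efforts to switch enzyme-inducing anticonvulsants in patients with gliomas or brain metastases. The protocol does not say whether case review can override the ban.

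The data at stake are the dose-finding and PK results. Under 5.1.1 a patient is evaluable for escalation after a DLT, or after at least 80% of planned doses and one full cycle without DLT. Interacting drugs play no part in that rule, so a patient with lowered exposure would count fully at the assigned dose level.

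**Working it through.** There is no stated figure to reproduce. The check compares three lists: the 5.3 strong inducers, the Appendix B CYP3A4 inducers and the Appendix B CYP3A4 inhibitors. The 5.3 spelling of rifapentine was matched to the Appendix B spelling, and rifampin (rifampicin) was counted once.

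**Step 1. Agents in 5.3 against the Appendix B inducer table**

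| Group in 5.3 | Named in 5.3 | In Appendix B inducer table | Omitted |
|---|---|---|---|
| Glucocorticoids | 5 | 0 | 5 (cortisone, hydrocortisone, prednisone, methylprednisolone, dexamethasone) |
| Anticonvulsants | 4 | 4 | 0 |
| HIV antivirals | 2 | 1 (nevirapine) | 1 (efavirenz) |
| Antibiotics | 3 | 3 | 0 |
| Miscellaneous | 4 | 1 (St. John's wort) | 3 (modafinil, pioglitazone, troglitazone) |
| Total | 18 | 9 | 9 |

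Share omitted: 9/18 = 50%. In the other direction, 14 − 9 = 5 agents are in the Appendix B table but not named in 5.3: aminoglutethimide, nafcillin, pentobarbital, primidone and fosphenytoin. The two lists together name 18 + 5 = 23 agents.

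**Step 2. Where the nine omitted agents appear elsewhere in Appendix B**

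- In the CYP3A4 inhibitor table: methylprednisolone, modafinil, efavirenz (3).
- Not in that table, but listed as a CYP2C19 inhibitor: pioglitazone (1). Modafinil and efavirenz are CYP2C19 inhibitors there too.
- In no Appendix B table: cortisone, hydrocortisone, prednisone, dexamethasone, troglitazone (5).

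3 + 1 + 5 = 9. Nevirapine is in both the CYP3A4 inducer and inhibitor tables, so it is not one of the nine.

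**Step 3. Direction of any effect on escalation**

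Under 5.1.1 a level is escalated after 0 of 3 DLTs, or after 1 of 3 followed by 0 of the next 3. Let p be the DLT risk at full exposure and q the risk of one under-exposed patient among the first three, with the next three at risk p:

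P(escalate) = (1−q)(1−p)² + [q(1−p)² + 2(1−q)p(1−p)] × (1−p)³

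The documents give neither p nor q, so the values below are assumptions that show direction only.

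| p | q = p | q = p/2 | q = 0.05 |
|---|---|---|---|
| 0.30 | 0.49 | 0.56 | 0.61 |
| 0.40 | 0.31 | 0.39 | 0.44 |
| 0.50 | 0.17 | 0.24 | 0.30 |

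For example, with p = 0.30 and q = 0.15: 0.85 × 0.49 + [0.15 × 0.49 + 2 × 0.85 × 0.30 × 0.70] × 0.343 = 0.4165 + 0.4305 × 0.343 = 0.56.

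**The case against.** The strongest reply is that the protocol already bans these drugs. Section 3.2.5 prohibits the class, Appendix B is a cross-reference and not the definition of what is banned, and 5.3 repeats the ban and names all nine omitted agents. Section 3.2.4 requires Principal Investigator review of interacting drugs. Section 3.2.16 excludes HIV-positive patients on combination antiretroviral therapy, which largely removes efavirenz and nevirapine. Section 4 adds an eligibility checklist and central confirmation. Four of the nine agents are flagged elsewhere in Appendix B, so a check there would still prompt review. All of this stands, and it limits the point to screening error. What it leaves open is that review starts only once a drug is recognised as interacting, that the pointers in 3.2.4 and 3.2.5 lead to Appendix B and not to 5.3, and that five agents, four of them glucocorticoids, are in no Appendix B table.

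A reader might infer that agents in the inhibitor table come under the exceptional-use allowance in 3.2.5. The documents do not support that. The allowance covers strong inhibitors, the strong-inhibitor lists in 3.2.5 and 5.3 do not name the three agents, and the Appendix B table is ungraded and includes acetaminophen and caffeine.

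It can also be argued that 3.2.4 and 3.2.5 fit together, with switching as the step by which a patient comes to satisfy the ban. That reading is possible, but the text does not state it.

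Finally, mandatory PK sampling (days 1 and 15 in escalation) could reveal low exposure, and at least 6 patients are required at the recommended dose. Both reduce the influence of one patient. Neither changes how that patient is counted under 5.1.1.

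**Conclusion.** The mismatch is exact: 9 of the 18 agents that 5.3 calls strong inducers are missing from the table that 3.2.5 cites, 3 of the 9 appear there as inhibitors, and nevirapine is in both tables. The softer wording in 3.2.4 and 5.3 adds to the uncertainty about how absolute the ban is.

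A reader might infer that the protocol lets patients on exposure-lowering drugs into the dose-finding cohorts. It does not: treating a patient on a drug that 5.3 lists as a strong inducer would breach the protocol. The supported conclusion is that staff who rely on Appendix B alone could miss a prohibited drug, most plausibly a glucocorticoid. Such use is foreseeable because 3.2.2 admits patients with stable treated brain metastases, but the documents give no frequency.

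A reader might also infer that the MTD will be set too high. Only the direction can be supported, and only if such a patient is enrolled, has lower exposure, and has a lower DLT risk as a result. The documents give no DLT rate and no size of induction, so the probabilities in the table above are illustrations and not estimates. No view is taken on which drug classification is right, or on whether a drug can belong to both classes.

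**What to change.** The sponsor should reconcile 3.2.4, 3.2.5, 5.3 and Appendix B so that:

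1. one strong-inducer list, with any dose thresholds, governs eligibility, and every section refers to it;
2. the text states whether case review under 3.2.4 can or cannot override the 3.2.5 prohibition, including for enzyme-inducing anticonvulsants;
3. the conflicting entries for methylprednisolone, modafinil and efavirenz (5.3 against Appendix B) and for nevirapine (within Appendix B) are resolved or explained.

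In the dose-level DLT and PK summaries, flag any patient who took a listed inducer during cycle 1. The study calendars already collect concurrent medications, so no new data are needed.

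The cost is a revised appendix table, a few sentences and one flag in the summaries. Depending on how the lists are reconciled, a few patients may become ineligible.
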